10.1 Brinzolamide 1% Suspension

10.1.1 Packaging and Labeling

The generic brinzolamide 1% suspension and brinzolamide 1% suspension (AZOPT®) will be provided by the Sponsor as 10 mL topical ophthalmic solutions. Each mL of the generic brinzolamide 1% suspension and Brinzolamide 1% suspension (AZOPT®) contains 10 mg of brinzolamide (1% w/v) and one drop of each medication (approximately 0.03 ml) contains approximately 0.3 mg of brinzolamide. The generic brinzolamide 1% suspension and brinzolamide 1% suspension (AZOPT®) will be supplied in eyedropper bottles that are in masked external packaging. Investigational product will be dispensed on Day 1 and on Day 21. Investigational product will be labeled according to local regulatory requirements with appropriate dosing and storage information as well as a unique container number that will be used to assign the medication to the subject according to their treatment assignment. Investigational product will be supplied in sufficient quantities to allow unopened containers to be kept as bioequivalence retains. Bioequivalence retains should be stored in accordance with protocol-specified requirements for at least 5 years following the date on which the application or supplemental application is approved, or, if such application or supplemental application is not approved, at least 5 years following the date of completion of a bioavailability or bioequivalence study. The quantity and storage of bioequivalence retains will be outlined in separate instructions to the site.

10.1.1.1 Retention of Study Drug Samples

At the time of receipt of the investigational product by the investigator, the sponsor will specify the appropriate number of containers or units to select for retention by the investigator. The total amounts of reserve samples will, at a minimum, be equivalent to five times the quantity of investigational product (test product and reference product) required for release testing. The total amount of reserve samples will be divided among all study sites participating in this study. The number of retain samples per site is subject to change, if the total number of sites change.

The sponsor will also specify the conditions of sample storage, the required duration of sample retention and the provisions for returning the investigational product. When retention samples are selected, containers or units should be placed in packaging with a tamper evident seal. The packaging should be clearly identified as to its content (that it contains retention samples) and the investigational product should be stored in a restricted area with limited access.

10.1.2 Storage, Handling, and Disposal of Study Drug

The investigator, or an approved representative, eg, pharmacist, will ensure that all investigational products, including any comparator and/or marketed products, are stored in a secured area with controlled access under required storage conditions in accordance with applicable regulatory requirements.

All investigational product must be stored at 4° to 30°C (39-86 °F) in accordance with the conditions specified on the study label. The storage location at the clinical site must have limited access, available to study site personnel only. Subjects must be instructed regarding proper storage. Investigational product should be stored in its original container and in accordance with the label.

Site systems must be capable of measuring and documenting (for example, via a log), at a minimum, daily minimum and maximum temperatures for all site storage locations (as applicable, including frozen, refrigerated and/or room temperature products) for business days only. This should be captured from the time of investigational product receipt

throughout the study. Even for continuous monitoring systems, a log or site procedure that ensures active daily evaluation for excursions should be available. The operation of the temperature monitoring device and storage unit (for example, refrigerator), as applicable, should be regularly inspected to ensure it is maintained in working order.

Any excursions from the investigational product label storage conditions should be reported upon discovery. The site should actively pursue options for returning the investigational product to the storage conditions as described in the labeling, as soon as possible. Deviations from the storage requirements, including any actions taken, must be documented and reported to the sponsor. Once an excursion is identified, the investigational product must be quarantined and not used until the sponsor provides documentation of permission to use the investigational product.

Specific details regarding information the site should report for each excursion will be provided to the site.

Receipt of materials, door opening and closing, and other routine handling operations where the investigational product is briefly out of the temperature range described in the labeling are not considered excursions. More specific details will be provided to the sites separately in an investigational product manual or equivalent, including storage conditions and actions to be taken when conditions are outside the specified range.

Investigational site staff will instruct subjects on the proper storage requirements for take home investigational products.

Retention samples of investigational product will be stored in accordance with Sponsor procedures and FDA regulations.

10.1.3 Study Drug Preparation and Dispensing

Investigational product should not be used more than 28 days after opening. It will be dispensed using ORS on Day 1 and Day 21 to ensure the subject has a sufficient amount of investigational product for the duration of treatment. A qualified and experienced member of the investigational site staff will dispense the investigational product in masked external packaging provided throughout the course of dosing. Investigational site staff must not be in

the room whenever the treatment is taken out of the masked external packaging. The bottle that is dispensed on Day 1 will be returned to the site in the masked external packaging on Day 21 (Visit 3), at which time a second bottle (again, in masked external packaging) will be dispensed to the subject; unused investigational product that was dispensed on Day 21 must be returned in the masked external packaging at the end of the Day 42 (Visit 4) (eg, after all assessments are performed). Note: The subject should also bring their bottle to Visit 2 for purposes of the in-office dose.

10.1.4 Administration

Administration instructions should be followed, which are on the investigational product label.

Each dose of investigational product (one eye drop) will contain 0.3 mg brinzolamide in either the generic brinzolamide 1% suspension or brinzolamide 1% suspension (AZOPT®).

One drop of investigational product should be instilled in each eye at approximately 8:00 AM, 4:00PM, and 10:00PM daily. On Day 1, the first day of dosing, only the 4pm and 10:00PM should be administered. On Day 42, the last day of dosing, only the 8:00AM dose is administered.

Subjects will self-administer investigational product daily on an outpatient basis; however, on Day 14, Day 21, and Day 42 the 8:00AM dose will be self-administered at the investigational site, following the 8:00AM IOP. The dose must be self-administered in a secluded room without any investigational site staff present within 30 minutes of 8:00 AM. Investigational site staff must not be in the room whenever the treatment is taken out of the masked external packaging or the subject is dosed with investigational product.

Subject knowledge and understanding of the dosing requirements must be verified before the subject leaves the investigator site at each visit.

10.2 Study Drug Accountability

The investigative site must maintain adequate records documenting the receipt, use, loss, or other disposition of the investigational product supplies. Unused investigational product that was dispensed on Day 1 must be returned in the masked external packaging to the

investigator at the Day 21 visit at which time another bottle (again, in masked external packaging) will be dispensed to the subject; unused investigational product that was dispensed on Day 21 must be returned in the masked external packaging at the end of the Day 42 visit (eg, after all assessments are performed and 8:00AM dose is instilled). The investigational site will employ procedures to avoid accidental unmasking of the masked staff. Investigational product accountability will be discussed in the study monitoring plan.

At various time points throughout the study and/or upon completion of the study, Valeant or representative of Valeant will review and verify the Investigator's accountability records. Following verification, and as directed by Valeant, all used and unused product must be returned to Valeant at the addresses below, or with Valeant's permission, disposed of at the site in an appropriate manner.

10.3 Destruction of Investigational Product Supplies

Following verification of investigational product accountability, and as directed by Sponsor, all used and unused product must be returned to [REDACTED], or with the Sponsor's permission, disposed of at the site in an appropriate manner.

11 Study Procedures and Evaluations

11.1 Schedule of Evaluations and Procedures

11.1.1 Screening Visit

Subjects will be screened from 4 to 42 days prior to administration of investigational product to confirm that they meet the subject selection criteria for the study. If the time between screening and dosing exceeds 6 weeks as a result of unexpected operational delays (eg, delayed drug shipment), then subjects do not require re-screening if at the baseline visit (Day 1) the patient meets the eligibility criteria.

The following procedures will be completed:

- Obtain informed consent;

- Obtain Subject Specific Identification
- Review inclusion/exclusion criteria;
- Collect demography;
- Complete medical history;
- Complete history of all prescription or nonprescription drugs, and dietary supplements taken within 30 days prior to signing the ICF;
- Blood pressure/pulse rate (sitting for 5 minutes);
- Visual field testing; if performed within 6 months (183 days) prior to screening and was documented in subject's records, no additional visual field testing is necessary
- Refraction
- Best corrected visual acuity;
- Collect Iris color: blue, brown, gray, green, hazel, or specify other;
- Biomicroscopy
- IOP
- Ophthalmoscopy
- Pachymetry
- Gonioscopy: (must use anesthesia): if performed within 6 months (183 days) prior to screening and was documented in subject's records, no additional screening gonioscopy examination is necessary
- Urine hCG for all females of childbearing potential;

If the subject meets the inclusion criteria:

- Discontinue topical and/or systemic ocular antihypertensives;

- Schedule the subject to return in 4 to 42 days (depending on washout time necessary for previous ocular hypotensive medication(s), Table 1, for the eligibility visit, Baseline (Day 1).
- Record any AEs that occur from the time the subject signs the ICF

To prepare for study participation, subjects will be instructed on use of Concomitant Medications ([Section 9.3](#)).

11.1.2 Visit 1 (Day 1)

Subjects must continue to satisfy all inclusion/exclusion criteria in order to be eligible for randomization.

The following procedures will be completed:

- Re-check inclusion/exclusion criteria (only those eligibility criteria that apply at Day 1);
- Review prior/concomitant treatments;
- Blood pressure/pulse rate (sitting);
- Best corrected visual acuity;

NOTE: Refraction must be performed if a decrease in VA of two or more lines from the previous assessment occurs.

- Biomicroscopy
- IOP at 8:00 AM \pm 30 minutes and 10:00 AM \pm 30 minutes;
- Ophthalmoscopy
- Assess and record adverse events (AEs);
- Urine hCG for all females of childbearing potential;
- Randomize the subject to a treatment group;

- To prepare for study participation, subjects will be instructed on the use of Concomitant Medications ([Section 9.3](#));
- Dispense dosing diary and instruct subject on completion;
- Dispense investigational product in masked external packaging and instruct subject on self-administration, storage, and return.
- First dose will be self-administered at 4pm, then followed by 10pm dose.

11.1.3 Visit 2 (Day 14)

The following procedures will be completed on Day 14 \pm 4 days:

- Review concomitant treatments;
- Check dosing diary;
- Blood pressure/pulse rate (sitting for 5 minutes);
- Best corrected visual acuity;

NOTE: Refraction must be performed if a decrease in VA of two or more lines from the previous assessment occurs.

- Biomicroscopy;
- IOP at \pm 30 minutes of 8:00 AM (prior to 8:00 AM dose of investigational product) and 10:00 AM. The 8:00 AM dose must be self-administered within 30 minutes of 8:00 AM in a secluded room without any investigational site staff present.
Investigational site staff must not be in the room whenever the treatment is taken out of the masked external packaging or the subject is dosed with investigational product. Subject knowledge and understanding of the dosing requirements must be verified before the subject leaves the investigator site at each visit
- Ophthalmoscopy
- Assess and record AEs.

11.1.4 Visit 3 (Day 21)

The following procedures will be completed on Day 21 \pm 4 days:

- Review concomitant treatments;
- Collect dosing diary, and dispense new dosing diary;
- Blood pressure/pulse rate (sitting for 5 minutes);
- Best corrected visual acuity;

NOTE: Refraction must be performed if a decrease in VA of two or more lines from the previous assessment occurs.

- Biomicroscopy;
- IOP at \pm 30 minutes 8:00 AM (prior to 8:00 AM dose of investigational product) and 10:00 AM. The 8:00 AM dose must be self-administered within 30 minutes of 8:00 AM in a secluded room without any investigational site staff present. Investigational site staff must not be in the room whenever the treatment is taken out of the masked external packaging or the subject is dosed with investigational product. Subject knowledge and understanding of the dosing requirements must be verified before the subject leaves the investigator site at each visit;
- Ophthalmoscopy
- Assess and record AEs;
- Collect the unused investigational product in the first bottle;
- Dispense investigational product in masked external packaging and instruct subject on the self-administration, storage, and return of product at visit 4.

11.1.5 Visit 4 (Day 42)

The subject has completed the study when Visit 4 (Day 42) has been completed and the subject has been exited. Subjects who require further follow-up for an AE will be followed according to Section [11.1.6](#).

The following procedures will be completed on Day 42 \pm 4 days:

- Review concomitant treatments;
- Check dosing diary;
- Collect dosing diary;
- Blood pressure/pulse rate (sitting for 5 minutes);
- Best corrected visual acuity;

NOTE: Refraction must be performed if a decrease in VA of two or more lines from the previous assessment occurs.

- Biomicroscopy;
- IOP at ± 30 minutes 8:00 AM (prior to 8:00 AM dose of investigational product) and 10:00 AM. The 8:00 AM dose must be self-administered within 30 minutes of 8:00 AM in a secluded room without any investigational site staff present. Investigational site staff must not be in the room whenever the treatment is taken out of the masked external packaging or the subject is dosed with investigational product. Subject knowledge and understanding of the dosing requirements must be verified before the subject leaves the investigator site at each visit;
- Ophthalmoscopy
- Assess and record AEs;
- Urine hCG for all females of childbearing potential;
- Collect the unused investigational product in the second bottle;

11.1.6 Post Study Follow-up Visit

A post study follow-up telephone call (conducted by the study coordinator or other delegated site staff) will occur approximately 28 days ± 4 days after the last dose of investigational product was taken. All outstanding unresolved adverse events and serious adverse events will be followed-up at this time. Concomitant treatments will also be recorded. The follow-up telephone call should be noted and documented in the subject's primary source records. If the subject had no new or ongoing adverse events, serious adverse events, or concomitant

treatments during this time, this should also be noted and added to the subject's primary source records. Any serious adverse event should be reported to Sponsor within 24 hours.

Every effort should be made to ensure that the protocol-required tests and procedures are completed as described. However, it is anticipated that from time to time there may be circumstances, outside of the control of the investigator that may make it unfeasible to perform a test. In these cases the investigator will take all steps necessary to ensure the safety and well-being of the subject. When a protocol-required test cannot be performed, the investigator will document the reason for this and any corrective and preventive actions that he or she has taken to ensure that normal processes are adhered to as soon as possible. The study team will be informed of these incidents in a timely fashion.

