To account for 10% attrition, approximately 624 subjects will be randomized in order to ensure that 560 subjects complete the 42 days (6 weeks) of dosing. Subjects who meet all inclusion/exclusion criteria will be randomized to receive the generic brinzolamide 1% suspension or brinzolamide 1% suspension (AZOPT®) using computer generated, blocked treatment assignments in a 1:1 ratio stratified by investigational site. Investigational product will be administered at approximately 8:00 AM, 4:00 PM and 10:00 PM in both eyes for 42 days, with exception of Visit 1 (Day 1) dose administered at only 4:00PM and 10:00PM. IOP assessments will be performed at approximately 8:00 AM and 10:00 AM on days 1 (baseline), 14, 21, and 42. IOP will be performed a second time (at approximately 10:00AM) on Days 1 (baseline), 14, 21, and 42. For subjects who discontinue the study before the end

of the treatment period, an Early Termination visit will be conducted within approximately one week after last study dose.

Figure 1 Study Design

[figure not shown]

Table 2 Study Design and Schedule of Assessments

Visit identifier	Screening	Visit 1	Visit 2	Visit 3	Visit 4	Early Termination
Visit Window	Day -42 to -4	Day 1	Day 14 ±4 days	Day 21 ±4 days	Day 42 ±4 days	Approximately within 7 days after last dose
Informed Consent	X					
Obtain Subject ID	X					
Randomization		X				
Inclusion/Exclusion criteria	X	X				
Demographics	X					
Medical History	X					
Prior and Concomitant medications	X	X	X	X	X	X
AE Monitoring	X	X	X	X	X	X
Check dosing diary			X	X	X	X
Collect unused investigational product				X	X	X
Collect dosing diary				X	X	X
BP and Pulse (sitting)	X	X	X	X	X	X
Visual Field Testing	X ^C					
Refraction	X	X*	X*	X*	X*	X*
BCVA	X	X	X	X	X	X
Biomicroscopy	X	X	X	X	X	X
Intraocular Pressure	X	X ^B	X ^B	X ^B	X ^B	X
Gonioscopy	X ^D					
Pachymetry	X					
Ophthalmoscopy	X	X	X	X	X	X
Urine Pregnancy Test	X	X			X	X
Dispense Investigational Product		X		X		
Dispense Dosing Diary		X		X		
Self-Administer Investigational Drug ^A			X ^A	X ^A	X ^A	

^A: indicates dosing will be self-administered at the site on visits 2, visit 3, and visit 4 after 8:00AM IOP measurement
^B: IOP measurement will occur twice (within ± 30 minutes of) 8:00AM and 10:00AM) at visit 1, visit 2, visit 3, and visit 4
^C: Visual Field testing to be conducted if no documentation within 6 months prior to screening
^D: Gonioscopy testing to be conducted if no documentation within 6 months prior to screening

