8.3 Subject Withdrawal Criteria

Withdrawal of consent: Subjects who wish to discontinue study treatment will remain in the study and must continue to be followed for protocol specified follow-up procedures. The only exception to this is when the subject specifically withdraws consent for any further contact with him or her or any persons previously authorized by the subject to provide information. Subjects are completely free to refuse to enter the study or to withdraw at any time, without giving a reason. The withdrawal of consent should be explained in detail in the medical records of the investigator, as to whether the withdrawal is only from further treatment of investigational product or also from study procedures and/or post treatment study follow-up, and entered on the appropriate CRF page. In the event that vital status (whether the subject is alive or dead) is being measured, publicly available information should be used to determine vital status only as appropriately directed in accordance with local law.

For subjects that are lost to follow-up, all reasonable efforts must be made to locate subjects to determine and report their ongoing status. This includes follow-up with persons authorized by the subject as noted above. Prior to discontinuing a subject, every effort should be made to contact the subject, schedule a final study visit, obtain as much follow-up data as possible, and to retrieve all study materials. All attempts should be documented in the subject's medical records. If it is determined that the subject has died, the site will use permissible

local methods to obtain the date and cause of death. If the investigator's use of a third-party representative to assist in the follow-up portion of the study has been included in the subject's informed consent, then the investigator may use a sponsor-retained third-party representative to assist site staff with obtaining the subject's contact information or other public vital status data necessary to complete the follow-up portion of the study. The site staff and representative will consult publicly available sources, such as public health registries and databases, in order to obtain updated contact information. If, after all attempts, the subject remains lost to follow-up, then the last-known-alive date as determined by the investigator should be reported and documented in the subject's medical records.

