12.1.2 Reporting Period

For SAEs, the active reporting period to Sponsor or its designated representative begins from the time that the subject provides informed consent, which is obtained prior to the subjects participation in the study, eg, prior to undergoing any study-related procedure and/or receiving investigational product, through and including 30 calendar days after the last administration of the investigational product. SAEs occurring to a subject after the active reporting period has ended should be reported to the Designee/Sponsor if the investigator becomes aware of them; but will not be entered on a case report form; at a minimum, all SAEs that the investigator believes have at least a reasonable possibility of being related to investigational product are to be reported to the Designee/Sponsor.

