Investigators should not wait to receive additional information to fully document the event before notifying Medical Monitor of an SAE. If only limited information is initially available, follow-up reports are required. Additional relevant information such as hospital records and autopsy reports should be provided to designee as soon as they are available. Should the investigator become aware of an SAE (regardless of its relationship to investigational product) that occurs within 30 days after stopping the study drug, the SAE must be reported in accordance with procedures specified in this protocol.

The investigator should take all appropriate measures to ensure the safety of the subjects, notably he/she should follow a subject with an SAE until the event has resolved or the condition has stabilized. This may imply that follow-up will continue after the subject has left the study, and that additional investigations may be requested by the sponsor.

The Designee will review forms and documents for completeness and forward to Sponsor within 24hrs of receipt via email: [REDACTED]

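### For completers, the only scheduled contact after the last-dose visit (a call at 28 ± 4 days) nominally comes 2 days, and at the earliest 6 days, before SAE reporting ends on day 30

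*Combined protocol and SAP*

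**What the plan says.** Two provisions of the protocol govern late SAE capture.

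- **Reporting period.** Under section 12.1.2, active SAE reporting "begins from the time that the subject provides informed consent" and runs "through and including 30 calendar days after the last administration of the investigational product". SAEs after that date are reported if the investigator learns of them. Section 12.2 uses the same 30-day limit. Section 12.6.1 softens it to approximately 30 days after the last dose or discontinuation.
- **Follow-up contact.** Section 11.1.6 says: "A post study follow-up telephone call (conducted by the study coordinator or other delegated site staff) will occur approximately 28 days". The section counts from the final dose and allows a tolerance of 4 days either way. At this call the site follows up unresolved events and documents whether anything new has arisen.

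For completers the last dose coincides with Visit 4. Section 10.1.4 states: "On Day 42, the last day of dosing, only the 8:00AM dose is administered". Section 11.1.5 treats the study as complete once that visit is done and the subject has been exited. Table 2 shows nothing after Visit 4 except the Early Termination column.

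Two other groups have different contacts. For subjects who leave the study early, "an Early Termination visit will be conducted within approximately one week after last study dose" (section 7.1). Subjects who only stop drug are kept on: "Subjects who wish to discontinue study treatment will remain in the study and must continue to be followed for protocol specified follow-up procedures" (section 8.3).

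**The concern.** The call is the plan's means of asking about events after treatment. If it takes place before the reporting period closes, the remaining days of that period have no scheduled enquiry. A new SAE in those days is recorded only if the site happens to hear of it, which is also how 12.1.2 treats SAEs after the period has ended.

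This is the result of following the nominal schedule, not of an unusual or non-compliant call. Comparing safety and tolerability is the study's secondary objective, so the period over which SAEs are meant to be collected should match the period over which sites are told to ask about them.

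**Working it through.** The plan states no figure for this gap, so there is none to reproduce. The check is calendar arithmetic with the last dose as day 0.

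**Inputs**
- Call: day 28 ± 4 (11.1.6).
- End of SAE period: day 30 inclusive (12.1.2; same limit in 12.2).
- Last dose for completers: Day 42, at Visit 4 (10.1.4); Visit 4 window ± 4 days (11.1.5).
- Start of SAE period: consent, taken at screening. Section 11.1.1 states: "Subjects will be screened from 4 to 42 days prior to administration of investigational product".

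**Gap by call day**

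Permitted call days: 28 − 4 = 24 to 28 + 4 = 32. Uncovered days = max(0, 30 − call day).

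| Call day | 24 | 25 | 26 | 27 | 28 | 29 | 30 | 31 | 32 |
|---|---|---|---|---|---|---|---|---|---|
| Uncovered days | 6 | 5 | 4 | 3 | 2 | 1 | 0 | 0 | 0 |

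Six of the nine permitted days (24 to 29) fall before day 30. A call on day 30 leaves only the rest of that day. Days 31 and 32 cover the period completely.

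**Gap as a share of the SAE period**

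Length of the whole period = s + (42 − 1) + 30, where s is the number of days from consent to Day 1.
- s = 4: 4 + 41 + 30 = 75 days.
- s = 42: 42 + 41 + 30 = 113 days.

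| Denominator | Nominal call (2 days) | Earliest call (6 days) |
|---|---|---|
| Whole period, 113 to 75 days | 2/113 to 2/75 = 1.8% to 2.7% | 6/113 to 6/75 = 5.3% to 8.0% |
| Post-dose segment, 30 days | 2/30 = 6.7% | 6/30 = 20% |

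If Visit 4 and the last dose fall at the window edges (Day 38 or Day 46), the whole period is 4 + 37 + 30 = 71 to 42 + 45 + 30 = 117 days. The shares become 1.7% to 2.8% and 5.1% to 8.5%.

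**Other subjects**
- Early discontinuers: a visit at about day 7 after the last dose is 30 − 7 = 23 days before day 30, and an earlier visit is further away. It does not close the gap.
- Drug stopped, subject stays in the study: a Visit 4 held on Day 42 is at least 31 days after the last dose only if that dose was on or before Day 42 − 31 = 11.

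No contact in the plan is tied to day 30 or later.

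**The case against.** The strongest reply is that nothing is contradicted. One section sets a reporting duty and the other schedules a call; a site can comply with both, and no section requires a contact to close the reporting period. The duty also survives the call. Section 12.2 covers this case: "Should the investigator become aware of an SAE (regardless of its relationship to investigational product) that occurs within 30 days after stopping" the drug, it has to be reported, and 12.6.1 says much the same. The limits are soft, since the call is at approximately 28 days and 12.6.1 speaks of approximately 30. Late calls cover everything. The gap is also unlikely to change a trial conclusion: section 13.3 compares only preferred terms reported by at least 5% of a group and tabulates the rest, and both arms follow the same call rule.

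Most of this stands. It is a design choice and not an inconsistency, no between-arm bias is shown, and no effect on the safety comparison has been demonstrated. The exact 2- and 6-day figures rest on 12.1.2 and 12.2, not on the looser wording of 12.6.1.

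What does not fall away is the missing enquiry. The sections that keep the duty alive depend on the investigator becoming aware of an event, and none of them prompts the site to ask about a new SAE after an early call.

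**Conclusion.** The point holds. For completers, the last scheduled enquiry about SAEs nominally precedes the end of the protocol's own SAE period by 2 days, and by up to 6 days within the permitted window.

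It is a modest weakness in ascertainment, confined to the last days after treatment. The conclusion rests on:
- the 30 calendar days in 12.1.2 as the end of the period;
- consent being given at the screening visit, 4 to 42 days before Day 1, for the percentage shares;
- reading the call as the only later contact after the Visit 4 day, since Visit 4 itself continues after the 8:00 AM dose.

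The number of SAEs that might be missed cannot be estimated because the documents give no SAE rate. The change is still worth making because it costs little and closes the gap for every compliant call.

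**What to change.** In 11.1.6, set the window of the same call so that it cannot fall before the SAE period has ended, for example day 33 ± 2, which is days 31 to 35 after the last dose. State the end of the SAE period in identical words in 12.1.2, 12.2 and 12.6.1.

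The cost is protocol wording only, with no extra contact. The nominal call, including its follow-up of unresolved adverse events, comes 33 − 28 = 5 days later, and the latest permitted call 35 − 32 = 3 days later.
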